### **7.5. Preparation/Handling/Storage/Accountability**

Only participants enrolled in the study may receive investigational product and only authorized site staff may supply or administer study treatment. All study treatments should be stored in an environmentally controlled and monitored (manual or automated) area in accordance with the labeled storage conditions with access limited to the investigator and authorized site staff.

The investigator, institution, or the head of the medical institution (where applicable) is accountable for study treatment accountability, reconciliation, and record maintenance (such as receipt, reconciliation, and final disposition records).

### **7.6. Treatment Compliance**

The investigational product, itraconazole, and placebo will be administered at the clinical site, and documentation of treatment administration will occur at the site.

### 7.7. Concomitant Therapy

Prohibited medications are summarized in the inclusion and exclusion criteria (Section 6). Use of vitamins/mineral supplements (not providing more than 100% of the RDA), thyroid hormone replacement, and/or estrogen hormone replacement is allowed. Occasional use of paracetamol/acetaminophen up to 2 g in a 24-period without prior consultation with a Lilly clinical pharmacologist will be allowed. Drugs that are known substrates, inducers, or inhibitors of CYP3A are specifically excluded. Additional drugs are to be avoided during the study unless required to treat an AE or for the treatment of an ongoing medical problem.

If the need for concomitant medication arises, inclusion or continuation of the subject may be at the discretion of the investigator after consultation with a Lilly clinical pharmacologist or CRP. Any additional medication used during the course of the study must be documented in the CRF.

## 8. Discontinuation Criteria

### 8.1. Discontinuation from Study Treatment

Subjects who discontinue the investigational product early will have procedures performed as shown in the Schedule of Activities (Section 2).

#### 8.1.1. *Discontinuation of Inadvertently Enrolled Subjects*

If the sponsor or investigator identifies a subject who did not meet enrollment criteria and was inadvertently enrolled, a discussion must occur between the Lilly clinical pharmacologist and the investigator to determine if the subject may continue in the study. If both agree it is medically appropriate to continue, the investigator must obtain documented approval from the Lilly clinical pharmacologist to allow the inadvertently enrolled subject to continue in the study with or without continued treatment with investigational product.

### 8.2. Discontinuation from the Study

Subjects will be discontinued in the following circumstances:

- Enrollment in any other clinical trial involving an investigational product or enrollment in any other type of medical research judged not to be scientifically or medically compatible with this study
- Participation in the study needs to be stopped for medical, safety, regulatory, or other reasons consistent with applicable laws, regulations, and good clinical practice
- Investigator Decision
  - the investigator decides that the subject should be discontinued from the study
- Subject Decision
  - the subject requests to be withdrawn from the study

Subjects who discontinue the study early will have end-of-study procedures performed as shown in the Schedule of Activities (Section 2).

### 8.3. Subjects Lost to Follow-up

A subject will be considered lost to follow-up if he or she repeatedly fails to return for scheduled visits and is unable to be contacted by the study site. Site personnel are expected to make diligent attempts to contact subject who fail to return for a scheduled visit or were otherwise unable to be followed up by the site.

## 9. Study Assessments and Procedures

Section 2 lists the Schedule of Activities, detailing the study procedures and their timing (including tolerance limits for timing).

Appendix 2 lists the laboratory tests that will be performed for this study.

Appendix 3 details the study governance, regulatory and ethical considerations.

Appendix 4 details the hepatic monitoring tests for treatment-emergent abnormalities.

Appendix 5 provides a summary of the maximum number and volume of invasive samples, for all sampling, during the study.

Unless otherwise stated in subsections below, all samples collected for specified laboratory tests will be destroyed within 60 days of receipt of confirmed test results. Certain samples may be retained for a longer period, if necessary, to comply with applicable laws, regulations, or laboratory certification standards.

Investigators must document their review of each laboratory safety report.

### 9.1. Efficacy Assessments

This section is not applicable for this study.

### 9.2. Adverse Events

Investigators are responsible for monitoring the safety of subjects who have entered this study and for alerting Lilly or its designee to any event that seems unusual, even if this event may be considered an unanticipated benefit to the subject.

The investigator is responsible for the appropriate medical care of subjects during the study.

The investigator remains responsible for following, through an appropriate health care option, AEs that are serious or otherwise medically important, considered related to the investigational product or the study, or that caused the subject to discontinue the investigational product before completing the study. The subject should be followed until the event resolves, stabilizes with appropriate diagnostic evaluation, or is reasonably explained. The frequency of follow-up evaluations of the AE is left to the discretion of the investigator.

After the informed consent form is signed, study site personnel will record, via CRF, the occurrence and nature of each subject's preexisting conditions. Additionally, site personnel will record any change in the condition(s) and the occurrence and nature of any AEs.

The investigator will interpret and document whether or not an AE has a reasonable possibility of being related to study treatment, or a study procedure, taking into account the disease, concomitant treatment, or pathologies.

A "reasonable possibility" means that there is a cause and effect relationship between the investigational product, study device, and/or study procedure and the AE.

Planned surgeries should not be reported as AEs unless the underlying medical condition has worsened during the course of the study.

If a subject's investigational product is discontinued as a result of an AE, study site personnel must report this to Lilly or its designee via CRF.

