## **7.3. Blinding**

This study will be subject- and investigator-blinded except in Part C (itraconazole interaction), which will be open-label. To preserve the blinding of the study, a minimum number of Lilly personnel will see the randomization table and treatment assignments before the study is complete. The randomization tables will be provided to the study site pharmacists or pharmacy staff involved in dose preparation.

As dosing occurs in the study, the pharmacy staff will document dosing at the site using an accountability log. Individuals involved with study drug preparation will not be involved in any clinical aspects of the study, including study drug administration and AE assessments. The sponsor team will not be blinded and may see the randomization tables and/or treatment table before the end of the study but this will be kept to a minimum. While the study blind is in effect,

individuals with access to the randomization tables and/or treatment table will not share the identifying information with investigative site staff involved with direct subject care or safety assessments. An exception is if sharing such information is required for emergency unblinding.

AEs and clinical safety abnormalities will be interpreted with the subject- and investigator-blind intact, on the assumption that active study drug was administered. If the AE is a clinically significant event (CSE), the investigator should judge whether the CSE is related to study drug administration while remaining blinded. A CSE will be defined as a moderate-to-severe AE, abnormal clinical sign, or clinical laboratory finding that may pose a risk to the well-being of the subject.

Emergency codes will be available to the investigator. A code, which reveals the treatment group for a specific study subject, may be opened during the study only if the subject's well-being requires knowledge of his/her treatment assignment.

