## **7.4. Dose Modification**

### **7.4.1. Dose Decision/Escalation**

By nature of being a dose-escalation study, data will be evaluated on an ongoing basis until the MTD is determined or the highest planned dose (that is lower than the MTD) has been administered. The highest dose level that is tolerated will be designated as the MTD.

Safety data will be the primary criteria for the dose escalation. As described in Sections 5.1.1.1 and 5.1.2.1, certain dose-escalation decisions will also be based on PK ( $C_{max}$ , AUC, and clearance) data where available. No dose escalation can occur without prior discussion and agreement between the investigator and the Lilly clinical pharmacologist/CRP/study team.

Safety data, in particular AEs, SAEs, and adverse laboratory abnormalities, will be independently assessed by the investigator, and will be considered related to the investigational product unless there is clear evidence that the event is not related. See Section 10.3.1 for details.

After review of these data, an agreement on the appropriate dose escalation will be made by the investigator and sponsor for the next cohort. The magnitude of the dose escalation may be reduced following data review, but subsequent escalations cannot be increased by more than 3.3 times the original dose (a half-log increment).

If any of the following scenarios occur, dosing at the current level and further dose escalation will be discontinued:

- 1) a single subject experiences an SAE that is considered related to LY3323795 administration;
- 2)  $\geq 2$  subjects at the same dose level experience moderate or severe AEs that impair normal activities, and are considered related to LY3323795, but do not meet the CSE criteria;
- 3)  $\geq 2$  subjects at the same dose level experience similar CSEs considered related to LY3323795;
- 4)  $\geq 2$  subjects at the same dose level have an ophthalmic finding considered related to LY3323795;
- 5)  $\geq 2$  subjects, at any dose of LY3323795, have a QTc reading (mean of 3) that is  $>500$  msec or an increase of  $>60$  msec above the mean QTc control value for at least 2 consecutive time points. The mean QTc control value (mean of 3) is defined as the average of the Day 1, predose ECGs of the corresponding period.

Dosing may continue, if deemed appropriate by the investigator and sponsor, at doses lower than those that resulted in the dose escalation being stopped.

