### **9.2.1. Serious Adverse Events**

An SAE is any AE from this study that results in 1 of the following:

- death
- initial or prolonged inpatient hospitalization
- a life-threatening experience (that is, immediate risk of dying)
- persistent or significant disability/incapacity
- congenital anomaly/birth defect
- events considered significant by the investigator based upon appropriate medical judgment

Study site personnel must alert Lilly, or its designee, of any SAE within 24 hours of investigator awareness of the event via a sponsor-approved method. If alerts are issued via telephone, they are to be immediately followed with official notification on study-specific SAE forms. This 24-hour notification requirement refers to the initial SAE information and all follow-up SAE information.

Investigators are not obligated to actively seek AEs or SAEs in subjects once they have discontinued from and/or completed the study (the subject summary CRF has been completed). However, if the investigator learns of any SAE, including a death, at any time after a subject has been discharged from the study, and he/she considers the event reasonably possibly related to the study treatment or study participation, the investigator must promptly notify Lilly.

Pregnancy (maternal or paternal exposure to investigational product) does not meet the definition of an AE. However, to fulfill regulatory requirements any pregnancy should be reported following the SAE process to collect data on the outcome for both mother and fetus.

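### Section 9.2 defines a reasonable possibility of relatedness as an actual causal link, so read literally it has events of uncertain cause documented as unrelated

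*Protocol*

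**What the plan says.** Protocol Section 9.2 asks the investigator to judge and document "whether or not an AE has a reasonable possibility of being related to study treatment, or a study procedure". It then states that a reasonable possibility "means that there is a cause and effect relationship between the investigational product, study device, and/or study procedure and the AE". The same section requires follow-up of several classes of AE, one of which is those "considered related to the investigational product or the study".

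Three other places bear on the same judgment:

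- Section 7.4.1 says that safety data, naming AEs, SAEs and adverse laboratory findings, are assessed by the investigator and "will be considered related to the investigational product unless there is clear evidence that the event is not related". It adds: "See Section 10.3.1 for details".
- Section 9.2.1 requires notification of an SAE learned of after discharge if "he/she considers the event reasonably possibly related to the study treatment or study participation". During the study, site staff "must alert Lilly, or its designee, of any SAE within 24 hours of investigator awareness of the event", whatever its cause.
- Section 7.3 has AEs in the blinded parts interpreted "on the assumption that active study drug was administered".

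The SAP gives no causality definition of its own. SAP Section 6.8.2 plans a summary of TEAEs judged related by the investigator. SAP Section 6.8.1 and Protocol Section 10.3.1.1 plan tables by perceived association and a count of product-related SAEs.

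**The concern.** A possibility is defined as an established fact. The investigator's answer is yes or no, and Section 9.2 has no category for uncertain cause. An event that might or might not be due to the drug does not meet the definition, so the answer falls to no. Many AEs after a single dose in a healthy volunteer are of this kind: plausible, but not provable.

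Four uses of the judgment are exposed:

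- the related-TEAE and association tables;
- the product-related SAE count;
- identification of SUSARs, which Section 9.2.1.1 ties to the investigator's attribution;
- follow-up of AEs that qualify only because they are judged related.

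This is a first-in-human study whose primary objective is safety and tolerability. A standard that understates relatedness errs in the less cautious direction.

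**Working it through.** The plan has no figure to reproduce here. The check compares the sections, traces where the judgment is used, and shows how sensitive the tables are.

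**One event of uncertain cause under each section**

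- Section 9.2, definition as written: a causal relationship must exist. It is not established, so the event is unrelated.
- Section 9.2, ordinary meaning of the term: a link is reasonably possible, so the event is related.
- Section 7.4.1: there is no clear evidence against a link, so the event is related.
- Section 9.2.1, post-discharge SAEs: the wording is a possibility standard, so the event is related, unless an investigator carries the 9.2 definition across.
- Section 7.3: the investigator assumes active drug was given. This settles exposure, not causality, and does not change the 9.2 answer.

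Sections 7.4.1 and 9.2 do not refer to each other, and neither says which governs. Section 7.4.1 points to Section 10.3.1, which sets no relatedness threshold.

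**What depends on the answer**

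- Exposed: the four uses listed in the concern. For follow-up, only AEs that are not serious, not otherwise medically important and did not cause discontinuation are affected, because the others are followed regardless.
- Protected: stopping criteria 1 to 4 in Section 7.4.1 require relatedness, but the presumption in that section applies. Criterion 5 (QTc) has no relatedness condition.
- Not exposed: TEAE incidence, the primary endpoint (Table SCAA.1), because Appendix 1 defines a TEAE without requiring causality; AE summaries that do not use relatedness; and 24-hour notification of on-study SAEs.

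**Scope** (inputs from Protocol Section 5.2)

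- Planned completers: 18 (Part A) + 21 (Part B) + 8 (Part C) = 47.
- Maximum enrolled: 24 + 30 + 12 = 66, approximately.
- The wording applies to active and placebo alike, since AEs in Parts A and B are judged blinded.

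**Sensitivity**

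The change in related-TEAE incidence when one subject is reclassified is 1/n, with n the group size:

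| Group | n | Change (percentage points) |
|---|---|---|
| Part A, one active dose | 6 | 1/6 = 16.7 |
| Part B, one active dose | 5 | 1/5 = 20.0 |
| Part C, one period | 8 | 1/8 = 12.5 |
| Part A, placebo within one dose level | 3 | 1/3 = 33.3 |
| Part B, pooled placebo | 3 × 2 = 6 | 1/6 = 16.7 |

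The documents do not say whether Part A placebo is tabulated by dose level or pooled. If pooled over 3 × 6 = 18 administrations, one administration moves the figure by 1/18 = 5.6 points.

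The number of subjects reclassified cannot be derived. The minimum is 0. The maximum is every subject whose only possibly related TEAEs are of uncertain cause.

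**The case against.** The best defence is that the literal reading takes one sentence alone. The operative task is to weigh a reasonable possibility in light of disease, other treatment and pathology. Section 9.2.1 uses possibility language, the tables report association as the investigator perceives it, and Section 7.4.1 presumes relatedness for events that the same investigator assesses. Section 7.4.1 also points to Section 10.3.1, which holds the association tables and the product-related SAE count, so the presumption may be meant to carry through to them. Investigators must report anything unusual and are trained on the protocol, and the sponsor reviews SAEs and AE trends (Section 9.4.5) and commits to SUSAR procedures consistent with global regulations. The 1/n figures would follow any single misclassification in a small group.

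Much of this stands as a limit on the consequence. A sensible investigator may never apply the definition, in which case the effect is zero. Missed expedited reporting is not shown. The 1/n figures are sensitivities, not expected effects.

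It does not cure the definition. Section 9.2 governs how AEs are documented, and no text in either document softens it. The pointer to Section 10.3.1 leads to no threshold. Training and sponsor review help, but they do not replace a correct written standard.

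**Conclusion.** The concern holds and is minor. As written, the definition in Section 9.2 is stricter than the term it defines and conflicts with Section 7.4.1; followed literally, it documents uncertain-cause events as unrelated.

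The size depends on which standard each investigator applies. Neither document gives an AE rate or the share of events of uncertain cause, so only the range from none to all such events can be stated. If the 7.4.1 presumption is carried into the related-event summaries, the effect there shrinks. The conclusion about the wording is firm; the practical effect is not established.

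**What to change.** In a protocol amendment, reword the defining sentence in Section 9.2 so that a reasonable possibility means that a causal relationship between the AE and the investigational product, study device or study procedure is possible and cannot reasonably be excluded. This restores the ordinary meaning, agrees with Section 9.2.1, and brings Section 9.2 close to Section 7.4.1, which needs no change. The two standards would still not be word for word the same.

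The cost is one sentence. Design, sample size, SAP methods and documentation stay as they are. Somewhat more events would be tabulated as related, on active and placebo, which is the cautious direction for first-in-human dosing.

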### **9.2.1. Serious Adverse Events**

An SAE is any AE from this study that results in 1 of the following:

- death
- initial or prolonged inpatient hospitalization
- a life-threatening experience (that is, immediate risk of dying)
- persistent or significant disability/incapacity
- congenital anomaly/birth defect
- events considered significant by the investigator based upon appropriate medical judgment

Study site personnel must alert Lilly, or its designee, of any SAE within 24 hours of investigator awareness of the event via a sponsor-approved method. If alerts are issued via telephone, they are to be immediately followed with official notification on study-specific SAE forms. This 24-hour notification requirement refers to the initial SAE information and all follow-up SAE information.

Investigators are not obligated to actively seek AEs or SAEs in subjects once they have discontinued from and/or completed the study (the subject summary CRF has been completed). However, if the investigator learns of any SAE, including a death, at any time after a subject has been discharged from the study, and he/she considers the event reasonably possibly related to the study treatment or study participation, the investigator must promptly notify Lilly.

Pregnancy (maternal or paternal exposure to investigational product) does not meet the definition of an AE. However, to fulfill regulatory requirements any pregnancy should be reported following the SAE process to collect data on the outcome for both mother and fetus.

#### **9.2.1.1. Suspected Unexpected Serious Adverse Reactions**

Suspected unexpected serious adverse reactions (SUSARs) are serious events that are not listed in the IB and that the investigator identifies as related to investigational product or procedure. United States 21 Code of Federal Regulations 312.32 and European Union Clinical Trial Directive 2001/20/EC and the associated detailed guidances or national regulatory requirements in participating countries require the reporting of SUSARs. Lilly has procedures that will be followed for the recording and expedited reporting of SUSARs that are consistent with global regulations and the associated detailed guidances.

### **9.2.2. Complaint Handling**

Lilly collects product complaints on investigational products and drug delivery systems used in clinical trials in order to ensure the safety of study participants, monitor quality, and to facilitate process and product improvements.

Subjects should be instructed to contact the investigator as soon as possible if he or she has a complaint or problem with the investigational product so that the situation can be assessed.

### **9.3. Treatment of Overdose**

For the purposes of this study, an overdose of LY3323795 is considered any dose higher than the dose assigned through randomization. General supportive medical management will be provided at the investigator's discretion.

Refer to the IB for LY3323795 for information on the clinical consequences of an overdose.

### **9.4. Safety**

#### **9.4.1. Laboratory Tests**

For each subject, laboratory tests detailed in [Appendix 2](#) should be conducted according to the Schedule of Activities (Section 2).

#### **9.4.2. Vital Signs**

Vital signs will comprise blood pressure, pulse rate, and body temperature.

For each subject, vital sign measurements should be performed according to the Schedule of Activities (Section 2). The timing of vital sign collections may be adjusted after a review of the PK data.

At screening, blood pressure and pulse rate will be obtained after subjects have been sitting for at least 5 minutes.

For vital signs after study entry, subjects will lie down for at least 5 minutes and undergo supine blood pressure and pulse rate measurements. For Parts A and C only, subjects will then sit for approximately 2 minutes and stand for approximately 3 minutes and undergo standing blood pressure and pulse rate measurements. If subjects are unable to stand, only supine vital signs will be recorded. If subjects are unable to stand or sit, omission of the standing or sitting vital signs will not be considered a protocol violation.

Subjects who are unable to sit or stand for approximately 3 minutes because of adverse symptoms should be placed immediately in a supine position with their legs elevated above the level of their chest. An unscheduled measurement of blood pressure and pulse rate should be obtained as soon as possible without causing delay in the resumption of recumbency.

Unscheduled orthostatic vital signs should be assessed, if possible, during any AE of dizziness or posture-induced symptoms. Additional vital signs may be measured during each study period if warranted.

